Objective 1 (Primary): Evaluate whether administration of THC-containing cannabis (versus placebo cannabis) subsequently influences self-administration patterns (time to first self-administration, amount consumed, puffing topography characteristics) of tobacco cigarettes or e-cigarettes.

Objective 2 (Primary): Evaluate whether administration of THC-containing cannabis (versus placebo cannabis) subsequently influences the acute effects (e.g., subjective effects) of tobacco cigarettes or e-cigarettes, nicotine withdrawal symptoms, or craving.

Objective 3 (Secondary): Evaluate whether administration of THC-containing cannabis (versus placebo cannabis) subsequently influences vital signs (e.g., heart rate, blood pressure).

Objective 4 (Secondary): Evaluate whether administration of THC-containing cannabis (versus placebo cannabis) subsequently influences cognitive performance.

3. Background (briefly describe pre-clinical and clinical data, current experience with procedures, drug or device, and any other relevant information to justify the research)

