Primary outcome variable is the amount of nicotine used (determined by total volume of cigarette smoke or JUUL vapor inhaled) after cannabis exposure in each session. We hypothesize that exposure to active cannabis will result in greater nicotine use compared with placebo cannabis.

b. Secondary outcome variables.

Secondary outcome variables include other nicotine use behaviors (amount self-administered and puff topography outcomes), subjective drug effect ratings, cognitive and psychomotor performance, and vital signs (HR, BP). We hypothesize that nicotine use will increase subjective drug effect ratings and decrease cognitive performance after exposure to active cannabis compared with the experimental session in which no nicotine/tobacco products are consumed. We also expect that active cannabis will increase self-reported drug effects compared with placebo cannabis.

c. Statistical plan including sample size justification and interim data analysis.

The proposed sample size of 40 study completers was estimated based on limited prior studies. One study found significant effects of transdermal nicotine and smoked cannabis on subjective drug effects with a sample size of N=20, suggesting that the proposed sample size for this study is adequate to detect interactive effects of nicotine and cannabis on subjective drug effects using a within subjects design (Penetar et al., 2005). Evaluation of pharmacodynamic drug effects using a within-subjects design reduces variability across dose administration sessions and significantly increases statistical power to detect differences on the proposed study outcomes. However, because we have a greater number of dose conditions, and because a primary outcome is amount of drug self-administration rather than self-reported drug effects, we expect the need for a greater sample size in this study.

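### The objectives make subjective effects, withdrawal, craving, topography and time to first use primary, but the statistics section has one primary variable, total inhaled volume, and no testing hierarchy

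*Combined protocol and SAP*

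**What the plan says.** Section 2 gives two primary objectives. Objective 1 asks whether active cannabis, compared with placebo, "influences self-administration patterns (time to first self-administration, amount consumed, puffing topography characteristics) of tobacco cigarettes or e-cigarettes". The second of the two begins: "Objective 2 (Primary): Evaluate whether administration of THC-containing cannabis (versus placebo cannabis) subsequently influences the acute effects (e.g., subjective effects) of tobacco cigarettes". Its remainder extends this to e-cigarettes, withdrawal and craving. Vital signs and cognition are Objectives 3 and 4, both secondary. The closing part of the Abstract (Section 1) also counts enhancement of the effects of nicotine products as part of the study's primary purpose, next to changes in self-administration.

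Study Statistics, part a, is narrower and defines the measure session by session: "Primary outcome variable is the amount of nicotine used (determined by total volume of cigarette smoke or JUUL vapor inhaled) after cannabis exposure in each". It attaches one hypothesis: "We hypothesize that exposure to active cannabis will result in greater nicotine use compared with placebo cannabis".

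Part b then states: "Secondary outcome variables include other nicotine use behaviors (amount self-administered and puff topography outcomes), subjective drug effect ratings", followed by cognition and vital signs. Craving, withdrawal and time to first use are not in that list.

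Part c sets a two-sided 0.05 level for all tests. It plans one active-versus-placebo t-test of consumption per nicotine product, then a comparison of the two e-cigarette strengths after active cannabis. Subjective ratings and craving come under secondary analyses, in a model with product and time as factors, fitted to the active-cannabis sessions only. No ordering of tests and no multiplicity adjustment is stated.

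**The concern.** Both sections are current text of the same document, and they give the same outcomes different status. Suppose consumption does not differ between active and placebo cannabis but a liking, satisfaction or craving score does. Section 2 would support reporting that a primary objective was met; Study Statistics would support calling it a secondary result. Nothing in the plan decides between them, and with every test at 0.05 the choice could be made after the data are seen. What is at stake is which result counts as confirmatory and what error rate stands behind it.

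**Working it through.** **Step 1. Status of each outcome in the two places.**

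| Outcome | Section 2 | Study Statistics |
|---|---|---|
| Amount used (total inhaled volume) | Primary (Obj. 1) | Primary (a) |
| Amount self-administered, no definition | not separated from amount consumed | Secondary (b) |
| Topography | Primary (Obj. 1) | Secondary (b) |
| Time to first use | Primary (Obj. 1) | not named |
| Subjective effects | Primary (Obj. 2) | Secondary (b, c) |
| Craving | Primary (Obj. 2) | Secondary analyses (c) only |
| Nicotine withdrawal | Primary (Obj. 2) | not named |
| Vital signs, cognition | Secondary (Obj. 3, 4) | Secondary (b, c) |

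The sections agree on the first and last rows only.

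**Step 2. A plan figure to reproduce.** There is none for error rate. The only planning figure is 40 completers, given without effect size, SD or power, so it cannot be re-derived.

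**Step 3. Error rate under the statistics section.** There are three product-specific t-tests (cigarette, 3% and 5% e-cigarette). If they are independent and there is no true effect, 1 − 0.95^3 = 0.143. Adding the 3% versus 5% comparison gives 1 − 0.95^4 = 0.185. With the three tests equally correlated at an assumed 0.3, 0.5 and 0.8, the figure is about 13-14%, 13% and 10%.

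**Step 4. Illustration for Objective 2.** Objective 2 lists no scores, so the count is an assumption drawn from the items named under Study Measures (Section 4a):
- Drug Effect Questionnaire: 7 items (drug effect, good effect, bad effect, liking, relaxed, paranoid, hungry)
- Direct Effects of Tobacco scale: 9 example items
- Craving questionnaires: 2

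That makes 7 + 9 + 2 = 18. The Drug Effect Questionnaire is directed mainly at cannabis effects; without it, 9 + 2 = 11.

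Assume one test per score, one active-versus-placebo contrast, no true effect and a common correlation ρ. The chance of at least one |z| > 1.96 among k tests is 1 − 0.95^k at ρ = 0. For ρ > 0 it is 1 − ∫ φ(x)·[Φ((1.96 − √ρ·x)/√(1−ρ)) − Φ((−1.96 − √ρ·x)/√(1−ρ))]^k dx.

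| k | ρ = 0 | 0.3 | 0.5 | 0.7 |
|---|---|---|---|---|
| 11 | 43% | 37% | 30% | 22% |
| 18 | 60% | 51% | 40% | 28% |

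**Step 5. Cost of adjusting the three primary tests.** Bonferroni gives 0.05/3 = 0.0167 per test. For a paired t-test with n = 40 (39 degrees of freedom) and 80% power, the detectable standardized paired difference rises from 0.45 to 0.53.

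**Step 6. Does a planned test answer Objective 2?** Objective 2 is an active-versus-placebo question. The model for subjective ratings and craving contains no placebo session, so it can compare products under active cannabis but cannot estimate that contrast.

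**The case against.** The best reply is that Study Statistics is the operative text. It names one variable, says how it is measured, states one hypothesis and gives its test. The sample-size text separates this outcome from self-report: "a primary outcome is amount of drug self-administration rather than self-reported drug effects". On that view Section 2 is only loosely labelled.

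Much of this stands. A reader might infer that almost any of dozens of tests could be called the primary result. The documents do not support that: under the statistics section the primary family is three t-tests, and vital signs and cognition are secondary throughout. A reader might also multiply the scores by three products to get 54 tests, but no active-versus-placebo test of these scores is planned.

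The no-effect assumption is also unsuitable for some items. Section 4a reports mean peak drug-effect ratings of 46 and 58 for the two active doses, and part b expects active cannabis to raise such ratings over placebo. Chance rates do not describe those contrasts.

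Finally, it is tempting to say that amount is listed as both primary and secondary. Part b places its amount measure among other nicotine use behaviors, which suggests something different from inhaled volume. The fair criticism is that it is undefined.

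The reply does not remove the conflict. Section 2 and the Abstract's statement of purpose both give effects primary standing, and the sample-size sentence speaks of a primary outcome, leaving room for others.

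**Conclusion.** The conflict is real and can be read directly from the current text. It concerns which outcomes carry primary status, and it leaves open whether a subjective or craving result may be claimed as primary when consumption is null. The size of the problem depends on the reading. Under the statistics section it is three unadjusted tests, about 14% if independent. If Objective 2 is taken as primary, an illustrative range for a single contrast is 43-60% under independence and 22-28% at correlation 0.7. The score counts, the single test per score, the correlations and the absence of a true effect are assumptions, not figures from the documents.

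Two related gaps would remain after relabelling: the three product tests have no stated combination or adjustment, and Objective 2's active-versus-placebo question has no matching analysis.

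**What to change.** Before analysis:

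1. In the Abstract's statement of purpose and in Section 2, make amount consumed, measured as total inhaled volume, the only primary outcome. Label time to first use, topography and all of Objective 2 secondary.
2. In Study Statistics, part b, add time to first use, and name craving and withdrawal so that the list matches Objective 2. Either define the amount self-administered as a measure distinct from inhaled volume or delete it.
3. State that no Objective 2 result will be reported as a primary finding.
4. In part c, say how the three product t-tests are combined or adjusted. With Bonferroni the detectable difference at 80% power moves from 0.45 to 0.53 SD of the paired difference.
5. Add the placebo sessions to the model for subjective ratings and craving, with cannabis condition as a factor. The no-nicotine session has no placebo counterpart, so the active-versus-placebo contrast rests on the six sessions with a nicotine product.

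Items 1 to 3 cost wording only, and Objective 2 loses its primary label. Item 4 costs some sensitivity if an adjustment is chosen. Item 5 uses data already scheduled for collection. Study conduct does not change.

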- a. Study design, including the sequence and timing of study procedures (distinguish research procedures from those that are part of routine care).

Protocol Overview. The proposed study will be conducted at the Johns Hopkins Behavioral Pharmacology Research Unit (BPRU). All participants will be healthy adult volunteers who are regular nicotine/tobacco users, and have prior experience with cannabis use. All procedures will be for research purposes.

Participants will complete seven outpatient experimental test sessions (see table below; completed in a randomized order), under double-blind conditions, in which they will first self-administer smoked cannabis (containing 10mg THC, 25mg THC or placebo), followed by access to their preferred brand of tobacco cigarette or a commercial e-cigarette device (e.g. JUUL) containing a 3% or a 5% nicotine solution for *ad libitum* self-administration. The dose of active cannabis will be determined based on the frequency of cannabis use prior to study participation. Individuals who report using cannabis >2 times per week on average in the 3 months prior to the study will be given an active cannabis dose of 25mg THC and participants reporting cannabis use ≤2 times per week on average will be given an active cannabis dose of 10mg THC. Prior research in our lab indicates that these doses will produce a moderate drug effect across all study participants. There will also be one condition in which participants smoke active cannabis and both cigarette and e-cigarette use will be prohibited during the test session. The seven experimental sessions will consist of:

- 1) Smoked cannabis containing 10mg or 25mg THC + No nicotine/tobacco
- 2) Smoked cannabis containing 10mg or 25mg THC + *ad-libitum* use of preferred brand cigarettes

Date: July 15, 2022

Principal Investigator: [name]

Application Number: IRB00220975

- 3) Smoked cannabis containing 10mg or 25mg THC + ad-libitum use of low nicotine content E-Cig (3% nicotine JUUL)
- 4) Smoked cannabis containing 10mg or 25mg THC + ad-libitum use of high nicotine content E-Cig (5% nicotine JUUL)
- 5) Smoked placebo cannabis + ad-libitum use of preferred brand cigarettes
- 6) Smoked placebo cannabis + ad-libitum use of low nicotine content E-Cig (3% nicotine JUUL)
- 7) Smoked placebo cannabis + ad-libitum use of high nicotine content E-Cig (5% nicotine JUUL)

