The Paced Auditory Serial Addition Task (PASAT) will measure working memory performance. Participants are shown a string of single digit integers and calculate the sum of each successive pair of integers presented; they select the correct answer from a list of displayed choices, ranging from 2-10. Each integer appears for 2.8 seconds during an initial set of 30 trials. After a 30-sec break, a second set of 60 additional trials is completed and integers appear every 2.4 seconds. Task duration is 5 min. PASAT outcomes include: total number of trials correct and reaction time on correct items (Gronwall, 1977). This task will be administered before (i.e., baseline), and approximately 5, 30, 60, 90, 120, 180, 240-and 360-min after cannabis exposure.

Date: July 15, 2022

Principal Investigator: [name]

Application Number: IRB00220975

The DRUID® app (“DRiving Under the Influence of Drugs”) has been developed as a novel screening tool to detect impairment from cannabis and other sources (e.g., alcohol). The DRUID requires users to perform four 30-45 sec tasks (total time is 2.5 min), measuring reaction time, decision making, hand-eye coordination, time estimation, balance, and/or divided attention. These performance domains are the most reliable predictors of driving impairment caused by cannabis/alcohol. Scores on each of the four tasks are summed to yield a global impairment score. This task will be administered before (i.e., baseline), and approximately 5, 30, 60, 90, 120, 180, 240-and 360-min after cannabis exposure.

b. Study duration and number of study visits required of research participants.

All potential participants will complete a visit for screening evaluation. Those who are eligible and enrolled in the study will complete seven experimental drug administration sessions, lasting approximately 6 hours each, and spaced 1 week apart. Because there are many experimental testing sessions in this trial, and interpretation of data is contingent on a complete data set, participants may be invited to repeat a study session should circumstances arise that result in the loss of data during a session (e.g. missing cognitive testing time points, equipment failure), or protocol deviation that impacts data integrity. This is not expected to occur for most participants.

c. Blinding, including justification for blinding or not blinding the trial, if applicable.

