Initial data analyses will examine whether study completers differ from non-completers with regard to demographic or cannabis use variables. This will inform the generality of the results. We will also examine the data for missing values. When missing data are found in self-report measures we will impute scores by averaging the closest pre and post values when applicable, otherwise missing data will be treated as missing in analyses. Missing data is expected to be rare given that all assessments are conducted via computer and individual items cannot be skipped. However, it is possible that a time point could be missed due to severe drug effects. Data will be evaluated for normal distribution, skewness, kurtosis and appropriate modifications will be made for data that is not normally distributed. All hypothesis tests will be two-sided; α will be set at 0.05. Nicotine/tobacco self-administration data will be analyzed using 2-tailed t-tests comparing the consumption of each nicotine/tobacco product after active versus placebo cannabis pre-treatment. Additional planned comparisons will then be conducted to compare consumption of 3% versus 5% nicotine E-Cig use following active cannabis. Secondary analyses will be conducted using repeated-measures multiple regression to evaluate the effects of nicotine/tobacco product type (None, conventional cigarette, low dose E-Cig, and high dose E-cig) and time as within-subjects factors on subjective drug effect ratings, cardiovascular effects, craving, and cognitive performance effects during sessions in which active (10mg or 25mg THC) cannabis was administered. If sufficient variability in pre-study cannabis use exists in our final study sample, we will conduct exploratory analyses comparing less frequent vs heavy (e.g. daily) cannabis users on primary and secondary outcomes.

d. Early stopping rules.

The study will be stopped if new information is learned that indicates a serious risk to study participants.

7. Risks

a. Medical risks, listing all procedures, their major and minor risks and expected frequency.

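### No analysis accounts for session number, so any trend over the seven weekly sessions adds avoidable noise to valid comparisons

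*Combined protocol and SAP*

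**What the plan says.** Section 4a (Protocol Overview) has every participant complete seven conditions, "completed in a randomized order". Three conditions pair active cannabis with a nicotine/tobacco product, three pair placebo cannabis with the same products, and one is active cannabis with no product. Section 4b gives "seven experimental drug administration sessions, lasting approximately 6 hours each, and spaced 1 week apart" and allows a session to be repeated if its data are lost. No section describes how orders are drawn, and none mentions a Latin or Williams square, blocking, or how a repeated session's place in the order is handled.

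Study Statistics, part a, defines the primary outcome as the amount of nicotine used, "determined by total volume of cigarette smoke or JUUL vapor inhaled". Part c specifies: "Nicotine/tobacco self-administration data will be analyzed using 2-tailed t-tests comparing the consumption of each nicotine/tobacco product after active versus placebo cannabis pre-treatment". The word paired does not appear; it is inferred from the within-subjects design. The secondary regression takes product type "and time as within-subjects factors on subjective drug effect ratings" and other pharmacodynamic outcomes, in the active-cannabis sessions. Time there most naturally means the assessment times within a session. No session-number, period or sequence term is named in either analysis.

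**The concern.** From the first to the last session is at least six weeks. Under inclusion criterion 11 (section 5) a participant may have used an e-cigarette only once in the past 30 days, yet four of the seven sessions use the JUUL. Puffing through the topography mouthpiece may also be new. Inhaled volume could therefore change as participants become familiar with the product or equipment.

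The DSST, PASAT and DRUID are given at baseline and eight later times in each session, so 9 × 7 = 63 times over the study. Practice gains are possible there, but those tasks are secondary outcomes and do not touch the primary t-tests.

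If a trend exists and the analysis ignores it, the within-participant difference between two conditions includes the trend multiplied by the gap in their session positions. That is removable noise. The sample size has no documented margin to absorb it, because the plan states no effect size, SD or power.

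**Working it through.** **Inputs from the documents.** k = 7 sessions; n = 40 completers; two-sided α = 0.05; three active-versus-placebo comparisons, read as paired.

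**Assumption.** A linear trend across sessions with total drift D from session 1 to session 7, in units of the SD of the paired difference without trend. The documents give no value, so a range is shown, starting at zero. The slope per session is D/6.

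**The plan's own figure.** The 40 completers cannot be reproduced: "The proposed sample size of 40 study completers was estimated based on limited prior studies", without an effect size, SD or power. Working backwards with the noncentral t distribution, a paired t-test with n = 40 has 80% power at a standardised difference of 0.454. That effect is the reference below.

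**Position gap.** When each order is equally likely, the gap in position between two conditions has mean 0 and variance

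2 × (k² − 1)/12 × k/(k − 1) = 2 × 4 × 7/6 = 9.33.

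Listing all 5,040 orders gives the same value. The SD is 3.06 per participant and √(9.33/40) = 0.48 sessions for the mean of 40.

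**Noise.** Variance inflation = 1 + 9.33 × (D/6)². The standardised effect becomes 0.454/√inflation.

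| Total drift D | Variance inflation | Power, t-test as planned | Completers needed to do the work of 40 |
|---|---|---|---|
| 0 | 1.000 | 80% | 40 |
| 0.3 | 1 + 9.33 × 0.0025 = 1.023 | 79% | 40.9 |
| 0.5 | 1 + 9.33 × 0.00694 = 1.065 | 77% | 42.6 |
| 1.0 | 1 + 9.33 × 0.0278 = 1.259 | 70% | 50.4 |

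**Validity.** In simulation with random order, no treatment effect and a drift of 0, 0.1 or 0.2 SD per session, the unadjusted t-test rejected in 4.4% to 5.0% of trials.

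**What recovers the loss.** Simulated power at the reference effect, random order, n = 40:

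- Adjusting the paired difference for the position difference by one linear term: 78.5% at 0.1 SD per session and 79.0% at 0.2. The unadjusted test has 76.4% and 66.7% (calculated). With no trend the cost is 79.5% to 78.4%, about one point.
- One model over the six nicotine/tobacco sessions (40 × 6 = 240 observations) with session number as a factor: about 80% at total drifts from 0 to 1.0.
- A six-parameter session factor inside each 40-participant comparison: about 72% to 73% whatever the drift. That is worse than the planned test at D = 0.5.
- Balanced (Williams) orders with the t-test left unadjusted: 77.1% and 68.4% at 0.1 and 0.2 SD per session, so little is gained. At 0.2 the type I error falls to 2.6%, because the trend stays in the standard error although the positions are balanced.

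**The case against.** The strongest reply is that random order already does what is needed: the comparison is unbiased, its standard error covers the noise, and any loss depends on a trend that no document shows. That stands. A reader might infer bias or an inflated error rate; the simulated type I error rules that out. A reader might also count the chance imbalance in session position as a second harm. It is the same quantity as the inflation: at D = 1.0, 0.483/6 = 0.08 and √(0.259/40) = 0.08.

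Second, the protocol acts against such trends. Section 4a (Recruitment) trains participants on the questionnaires and tasks, and instructs them on the pipe and on the products fitted with topography equipment, before they are invited to continue. One of the three primary comparisons uses the participant's own brand, and each session starts with an observed cigarette. This should make the drift smaller. It does not show the drift to be zero over seven sessions, least of all for participants who rarely use e-cigarettes.

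Third, a reader might take the text to mean that orders are unconstrained. The documents say only that the order is randomised, and a balanced list would fit that wording. This changes little: balance without a session term leaves most of the noise in the t-test.

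**Conclusion.** The concern holds as a matter of efficiency only. The tests as planned are valid. The plan leaves out a standard term that would protect power if outcomes drift over the sessions. The loss is under one power point at a total drift of 0.3 SD, about three points at 0.5 SD and about ten at 1.0 SD. These figures rest on an assumed linear trend, on the tests being paired, and on a reference effect chosen to give 80% power, because the plan names none. For the primary outcome the plausible source is familiarity with product or equipment. Practice on the cognitive tasks bears on secondary outcomes alone. With pre-session training in place the smaller drifts are easier to believe, so the change is worth making mainly because it is cheap.

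**What to change.** In Study Statistics, part c, do one of the following for the primary outcome:

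- Replace the separate t-tests with one mixed model over the six nicotine/tobacco sessions, with participant as a random effect, condition and session number as factors, and the three active-versus-placebo contrasts estimated within it.
- Keep three comparisons, state that they are paired, and adjust each for the difference in session position by a single linear term. Do not fit a six-parameter session factor within each comparison.

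Add session number to the secondary regression. Use the position actually occupied by any repeated session, and say how an eighth visit is coded.

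State in section 4a how orders are generated. A Williams list (14 sequences for seven conditions) is an option. Forty is not a multiple of 14, so balance would be approximate (42 would be exact), and the extra gain is small. If participants are already randomised, the model term alone brings most of the benefit.

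Cost: no extra visits or participants, and about one power point or less if there is no trend. The pooled model assumes a common error variance for cigarettes and e-cigarettes; product-specific variances should be allowed if that is doubtful.

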Experimental Drug Exposure. After completion of baseline procedures, approximately 1 hour after the baseline cigarette, participants will self-administer a fixed amount of smoked cannabis, precisely weighed to contain either 0 (placebo), 10 mg THC (active for those who use cannabis \leq 2 times/week), or 25 mg THC (active for those who use cannabis $>$ 2 times/week). Cannabis will be smoked using a custom pipe, fitted with a large “bowl” and screw cap that obscures the contents of the pipe to both the study participants and staff, thereby maintaining the study blind. To ensure complete dose delivery, participants will smoke the pipe until all the plant material has been combusted. We have used this method of cannabis administration in prior studies (Spindle, 2018) to produce orderly dose effects on pharmacodynamic outcomes. The 10 mg and 25 mg THC doses were chosen to balance participant safety and tolerability while maximizing the ability to detect modulation of drug effects by nicotine co-administration in each respective cannabis-use population (i.e., intermittent users who use cannabis \leq 2 times/week and heavy users who use cannabis $>$ 2 times/week). In a recent study of ours (Spindle, 2018), a smoked 10 mg THC dose administered to healthy adults who were intermittent cannabis users, produced a moderate drug effect (Mean peak VAS “Drug Effect” rating = 46 of a possible 100), but no adverse events or untoward drug effects. In another recent study in our laboratory (IRB00101744) that included heavy cannabis users, a smoked 25 mg THC dose produced a moderate drug effect (Mean peak VAS “Drug Effect” rating = 58 of a possible 100) and no adverse events or untoward drug effects were observed. We believe that adjusting the THC dose to account for tolerance to the acute effects of THC in more frequent cannabis users is critical to providing ecologically valid data, and that keeping the dose delivered constant across sessions is critical to the rigor of the study and interpretation of the study findings.

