Principal Investigator: [name]

Application Number: IRB00220975

To determine eligibility, the clinical assessments conducted during the screening process will be reviewed by study physicians with JHBMC privileges (e.g., Drs. [name], [name]) and psychological assessments and full inclusion/exclusion criteria will be reviewed by [name] or another senior Co-investigator (e.g., [name]). [name] or other JHBMC credentialed study physician will review all health information to determine study eligibility. [name] is a board certified internist with 14 years of experience with research participants at the BPRU, including cannabis users.

6. Drugs/ Substances/ Devices

a. The rationale for choosing the drug and dose or for choosing the device to be used.

Participants will smoke a fixed dose of cannabis (containing either 10mg or 0mg THC) using a small commercial pipe. Placebo (<1% THC by dry weight) and active cannabis (approximately 10-13% THC by dry weight) will be obtained from the NIDA drug supply program for this study. All cannabis will be precisely prepared and dispensed by the BPRU pharmacy. Participants will be given the pipe and instructed to smoke its entire contents *ad-libitum* (i.e., at their own pace), within 10 minutes. The pipe will be fitted with a metal top to obstruct the participants' and experimenters' view of its contents. This procedure has been demonstrated to reliably deliver doses of THC from dried cannabis and adequately blinds study conditions (Spindle, 2018).

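### Section 6a gives 10 mg or 0 mg THC in a small commercial pipe, which contradicts the 10 mg or 25 mg rule and the custom large-bowl pipe in section 4a

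*Combined protocol and SAP*

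**What the plan says.** Section 6a (Drugs/ Substances/ Devices) states: "Participants will smoke a fixed dose of cannabis (containing either 10mg or 0mg THC) using a small commercial pipe". It adds a metal top that hides the contents and gives the potency of the active material as roughly 10-13% THC by dry weight. It says the unit's pharmacy prepares and dispenses all cannabis, and sets a 10-minute limit for smoking it. Further on, the same section reports a 25 mg result in heavy users, but only from a previous study. The 10 mg dose is the only one it describes as having been chosen for this trial.

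Section 4a, Protocol Overview, says that "they will first self-administer smoked cannabis (containing 10mg THC, 25mg THC or placebo"), with the active dose set by use over the previous 3 months. Those above 2 uses per week "will be given an active cannabis dose of 25mg THC and participants reporting cannabis use ≤2 times per week on average" receive 10 mg. The list of active sessions repeats 10 mg or 25 mg.

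Section 4a, Experimental Drug Exposure, restates the rule: "participants will self-administer a fixed amount of smoked cannabis, precisely weighed to contain either 0 (placebo), 10 mg THC" for the less frequent users, or 25 mg for the more frequent. On the device it says: "Cannabis will be smoked using a custom pipe, fitted with a large “bowl” and screw cap that obscures the contents of the pipe". It credits this cover with keeping both sides blind.

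Participant Discharge (section 4a), the statistical plan (Study Statistics, c) and the steps to minimize risk (section 7b) all take 10 mg or 25 mg as the study doses. Section 7a speaks of the administered cannabis dose in the singular.

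**The concern.** The administered dose is a figure the trial relies on. It defines the active level of the primary contrast, which is nicotine or tobacco consumption after active versus placebo cannabis for each product. It also bears on participant safety. Two current sections give different active doses for the same people, those above 2 uses per week. Section 4a calls adjusting the dose for tolerance critical to ecological validity, while the dosing sentence in section 6a contains no adjustment.

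The exploratory comparison of less frequent with heavy cannabis users is affected too. Under section 4a, users at or below 2 times per week and daily users receive different active doses, so dose and use history vary together. Under section 6a they receive the same dose, and the comparison answers a different question.

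The device also differs, being small and commercial in one place and custom with a large bowl in the other. Both sections cite the same earlier smoked-cannabis study in support of the method.

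**Working it through.** The plan states no figure to reproduce on this point. The check is a comparison of the texts plus one calculation.

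**Side by side**

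| Place | Active dose for this trial | Device |
|---|---|---|
| 4a, Protocol Overview | 10 mg (≤2 uses/week) or 25 mg (>2 uses/week) | not described |
| 4a, Experimental Drug Exposure | same rule | custom pipe, large bowl, screw cap |
| 4a, Participant Discharge | 10 mg or 25 mg | not described |
| 6a, dosing sentence | 10 mg | small commercial pipe, metal top |
| 6a, later text | 10 mg chosen; 25 mg as prior-study data only | not described |
| Study Statistics, c | 10 mg or 25 mg | not described |
| 7a | one dose, unspecified | not described |
| 7b | 10 mg or 25 mg | not described |

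For a participant at or below 2 uses per week, sections 4a and 6a agree on 10 mg. For a participant above 2 uses per week they give 25 mg and 10 mg. No text links or reconciles them, and both are current text, not entries in a change log.

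**Size of the difference**

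Inputs: doses of 10 mg and 25 mg (section 4a); potency 10% to 13% by dry weight (section 6a).

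Ratio of active doses: 25 / 10 = 2.5.

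Plant mass = THC dose / potency:

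- 10 mg: 10 / 0.13 = 76.9 mg and 10 / 0.10 = 100 mg
- 25 mg: 25 / 0.13 = 192.3 mg and 25 / 0.10 = 250 mg

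The load is thus about 77-100 mg under one text and 192-250 mg under the other, 2.5 times as much at equal potency. The documents give no pipe capacity, so these masses cannot show whether either pipe suits either load.

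**Effect on the analysis**

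The primary tests are two-tailed t-tests of active versus placebo within each product. Their form, the two-sided alpha of 0.05 and the target of 40 completers do not depend on which dose text is followed. Only the exposure labelled active changes. The expected share of participants above 2 uses per week is not given, so the 2.5-fold difference cannot be converted into an effect on the primary contrast.

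**The case against.** The strongest reply is that one sentence stands alone against five places that agree: two passages of the procedures, the discharge text, the statistical plan and the risk section. Section 6a is headed as a rationale for drug, dose and device, and its remark about the pharmacy is not a preparation instruction. Staff would have to dose from that sentence while disregarding the procedures for the session. This stands as an argument about likelihood: misdosing is a possibility, not an expected outcome. It does not remove the contradiction, and agreement among passages does not by itself settle which is right. Nor can section 6a be set aside as background, because it is the only place that gives the potency and the 10-minute limit.

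A reader might infer that the pipe conflict undermines the blind, or that a larger load could not be masked. The documents do not support this. Section 4a has a screw cap and section 6a a metal top; each hides the contents from participants and staff. No placebo plant mass or pipe capacity is stated. Section 4a also keeps each participant's active dose constant across sessions, so no one is meant to compare a 10 mg load with a 25 mg load.

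A reader might also infer that 25 mg is missing from section 6a altogether. It is cited there, but only as evidence from another study.

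**Conclusion.** The plan is wrong as written on this point: an internal inconsistency of low severity. The dosing sentence in section 6a conflicts with the assignment rule in section 4a for every participant above 2 uses per week, by a factor of 2.5, and the two sections describe the pipe in incompatible terms. The plant-mass ranges rest on the stated, approximate 10-13% potency.

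What depends on the resolution is the meaning of active cannabis in the primary comparison and in the exploratory comparison by use frequency. Sample size, alpha and the planned tests are unaffected. The text supports neither a failure of blinding nor a prediction that participants will be misdosed.

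**What to change.** Reconcile section 4a (Protocol Overview and Experimental Drug Exposure) with section 6a so that the dose levels, the assignment rule and the pipe are stated identically. Check the remaining dose references at the same time: Participant Discharge, the prior-study paragraph in section 6a, Study Statistics c, the singular reference in section 7a, and section 7b. Confirm that the dispensing instructions held by the pharmacy match the reconciled text, and state whether the 10-minute smoking limit applies to every dose retained.

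Which version is correct is for the investigator and sponsor to say; this review takes no view. The cost is a wording amendment and a check of the dispensing documents, with no change to sample size or analysis.
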